9.9.9.1.6. Relationship

The Investigator (or designee) will make a determination of the relationship of the AE to the study drug using a 4-category system according to the following guidelines:

Not Related: The AE is definitely caused by the subject's clinical state or the study

procedure/conditions.

Unlikely Related: The temporal association between the AE and the drug is such that the

drug is not likely to have any reasonable association with the AE.

Probably Related: The AE follows a reasonable temporal sequence from administration of

the drug and cannot be reasonably explained by the known

characteristics of the subject's clinical state, environmental, or toxic

factors, or other modes of therapy administered to the subject.

Related: The AE follows a reasonable temporal sequence from administration of

the drug, abates upon discontinuation of the drug, follows a known or hypothesized cause-effect relationship, and (if appropriate) reappears

when the drug is reintroduced.

The Investigator will use clinical judgement to determine the relationship. Alternative causes, such as underlying disease(s), concomitant therapy, and other risk factors, as well as the temporal relationship of the event to the study treatment administration should be considered and investigated. The Investigator should consult the IB and the Product Information of marketed products within the drug class, when applicable. For each adverse event/SAE, the Investigator must document in the medical notes that he/she has reviewed the adverse event/SAE and has provided an assessment of causality. There may be situations in which an SAE has occurred and the Investigator has minimal information to include in the initial report to the Sponsor; however,

it is very important that the Investigator always make an initial assessment of causality for every event before the initial transmission of the SAE to the Sponsor. The Investigator may change his/her opinion of causality based on subsequent receipt of information and send an SAE follow-up report with the updated causality assessment. The causality assessment is one of the criteria used when determining regulatory reporting requirements.

9.9.9.2. Eliciting and Recording Adverse Events

9.9.9.2.1. Eliciting Adverse Events

Subjects will be instructed that they may report adverse events at any time. An open-ended or nondirected method of questioning should be used at each study visit to elicit the reporting of adverse events.

9.9.9.2.2. Recording Adverse Events

The adverse event reporting period for safety surveillance begins when the subject is initially included in the study (date of first signature of informed consent) and continues up to 30 days after the last administration of study treatment. If an adverse event is not resolved or stabilized by this time, the Sponsor in consultation with the Investigator will decide whether to continue to monitor the adverse event or closeout the event in the database if no further follow-up is necessary.

Investigators are not obligated to actively seek information on AEs or SAEs after the subject has concluded study participation. Any SAE suspected to be related to the study treatment must be reported whenever it occurs, irrespective of the time elapsed since the last administration of study treatment.

Investigators and study personnel will record all adverse events and SAEs whether received through an unsolicited report by a subject, elicited during subject questioning, discovered during physical examination, laboratory testing, and/or other means by recording them on the eCRF and/or SAE Form, as appropriate. The following information should be recorded on the adverse event eCRF:

- Description including onset and resolution dates
- Whether it met SAE criteria
- Severity
- Relationship to study treatment or other causality
- Outcome

For SAEs, events occurring secondary to the primary event should be captured and reported via the established safety reporting mechanism.

The following should be considered when recording SAEs:

- Death is an outcome of an event. The event that resulted in the death should be recorded and reported on the eCRF.
- For hospitalizations, surgical, or diagnostic procedures, the illness leading to the surgical or diagnostic procedure should be recorded as the SAE, not the procedure

itself. The procedure should be captured in the narrative as part of the action taken in response to the illness.

9.9.9.2.3. Diagnosis Versus Signs or Symptoms

In general, the use of a unifying diagnosis is preferred to the listing out of individual symptoms. Grouping of symptoms into a diagnosis should only be done if each component sign and/or symptom is a medically confirmed component of a diagnosis as evidenced by standard medical textbooks. If any aspect of a sign or symptom does not fit into a classic pattern of the diagnosis, report the individual symptom as a separate adverse event.

9.9.9.3. Reporting Adverse Events

All SAEs are subject to reporting requirements.

9.9.9.3.1. Serious Adverse Events

Any adverse event considered serious by the Investigator or Sub-Investigator or that meets serious criteria should be reported to the designated safety contact within 24 hours of becoming aware of the event. Enter the SAE information into eCRF and send all available pertinent information to the designated Sponsor Contact via established reporting mechanism.

IQVIA Pharmacovigilance

[contact]

[contact]

E-mail (preferred method): [contact]

If additional information is required or becomes available for a previously reported SAE, entry of the new information into eCRF and forwarding of all available pertinent information to the designated Sponsor Contact via established reporting mechanism should be completed within 24 hours of awareness.

Elective hospitalization and/or surgery for clearly preexisting conditions (eg, a surgery that has been scheduled prior to the subject's entry into the study) will not be reported as an SAE.

Any SAE that is ongoing when the subject completes the study or discontinues the study will be followed by the Investigator until the event resolved, stabilized or returned to baseline status.

9.9.9.3.2. Serious, Unexpected Adverse Drug Reactions

All ADRs that are both serious and unexpected are subject to expedited reporting to regulatory agencies. An unexpected ADR is one for which the nature or severity is not consistent with information in the relevant source documents.

Since etrasimod is an investigational medicinal product that has not yet been approved for marketing in any country, the current edition of the IB in effect during the study will serve as the Reference Safety Information for determining whether an AE is expected or unexpected.

9.9.10. Pregnancy and Lactation

9.9.10.1. Pregnancy

If at any point a serum β -hCG pregnancy test is positive, the subject will be withdrawn from the study treatment.

Details of all pregnancies in female subjects and female partners of male subjects will be collected after the start of study treatment and until 30 days after the last dose.

Pregnancy (during maternal or paternal exposure to study treatment) does not meet the definition of an adverse event; however, to fulfill regulatory requirements, any pregnancy and/or pregnancy outcome should be reported via the established reporting mechanism (eg, pregnancy reporting form) to the designated Sponsor Contact within 24 hours of awareness to collect data on the pregnancy and on the outcome for both the mother and the fetus.

Abnormal pregnancy outcomes (eg, spontaneous abortion, fetal death, stillbirth, congenital anomalies, ectopic pregnancy) are considered SAEs and should be reported as such (following the SAE reporting process) even if outside the SAE reporting period.

9.9.10.2. Exposure During Breastfeeding

An exposure during breastfeeding (EDB) occurs if:

 A female subject is found to be breastfeeding while receiving or after discontinuing study treatment.

Exposure during breastfeeding does not meet the definition of an adverse event; however, to fulfill regulatory requirements, should be reported via the established reporting mechanism to the designated Sponsor Contact within 24 hours of awareness to collect data on the exposure and on the outcome for both the mother and the child.

9.9.11. Environmental Exposure

Environmental exposure occurs when a person not enrolled in the study as a subject receives unplanned direct contact with or exposure to the study treatment. Such exposure may or may not lead to the occurrence of an AE or SAE. Persons at risk for environmental exposure include healthcare providers, family members, and others who may be exposed. An environmental exposure may include exposure during pregnancy (EDP), EDB, and occupational exposure.

Examples of environmental exposure may include oral ingestion of, inhalation of, or skin contact with a tablet that is broken/crushed.

Any such exposures to the study treatment are reportable to the designated Sponsor Contact via established reporting mechanism within 24 hours of Investigator awareness, irrespective of whether an AE has occurred.

9.9.11.1. During Pregnancy

An environmental exposure during pregnancy (EDP) occurs if:

 A female nonparticipant is found to be pregnant while being exposed or having been exposed to study treatment because of environmental exposure. A male nonparticipant who has been exposed to the study treatment then inseminates his female partner prior to or around the time of exposure.

9.9.11.2. During Breastfeeding

An environmental exposure during breastfeeding (EDB) occurs if:

 A female nonparticipant is found to be breastfeeding while being exposed or having been exposed to study treatment.

9.9.11.3. Occupational

The Investigator must report any instance of occupational exposure and all available pertinent information to the designated Sponsor Contact via established reporting mechanism within 24 hours of the Investigator's awareness, regardless of whether there is an associated AE. Since the information about the occupational exposure does not pertain to a subject enrolled in the study, the information is not recorded on a CRF; however, a copy of the completed SAE reporting form must be maintained in the Investigator site file.

9.9.12. Lack of Efficacy

The Investigator must report signs, symptoms, and/or clinical sequelae resulting from lack of efficacy. Refer to Section 5.1 for circumstances which may lead to discontinuation from study treatment. Lack of efficacy or failure of expected pharmacological action is reportable to the designated Sponsor Contact only if associated with an SAE.

9.9.13. Medication Errors

Medication errors may result from treatment administration by the wrong subject.

Whether or not the medication error is accompanied by an AE, as determined by the investigator, the medication error and potentially associated AE/SAE are recorded in the eCRF. SAEs must be reported to the designated Sponsor Contact via established reporting mechanism within 24 hours of awareness.

9.10. Procedures for Overdose

The current edition of the IB should be referenced for overdose procedures.

There is no established overdose threshold for this clinical study, nor is there any recommended specific treatment for an overdose but to provide supportive care if clinically indicated.

In the event of a suspected overdose, the Investigator and/or treating physician should:

- Closely monitor the subject for any AE/SAE and laboratory abnormalities and follow the AE reporting process, including contacting the Medical Monitor
- Obtain a plasma sample for PK analysis within 7 days from the date of the last dose of study treatment, if possible, and if requested by the Medical Monitor
- Document the total quantity of the excess dose, taking into consideration the duration of the overdose in the eCRF and the time frame

Subjects who overdose will be counseled on correct dosing and administration of study treatment. Decisions regarding study discontinuation, dose interruptions, or dose modifications will be made by the Investigator in consultation with the Medical Monitor based on the clinical evaluation of the subject.

10. PLANNED STATISTICAL METHODS

10.1. General Considerations

All individual subject data for all randomized subjects will be presented in data listings. All efficacy and safety endpoints will be summarized by treatment group. Full details of the statistical considerations and planned analyses will be described in the study Statistical Analysis Plan (SAP).

10.2. Determination of Sample Size

Based on a 2-group Fisher's exact test, a two-sided significance level of 0.05, and a 2:1 randomization ratio, approximately 183 subjects (122 etrasimod, 61 placebo) are required to achieve at least 80% power to detect a difference of 20% in the primary endpoint of clinical remission (based on MMS) at Week 52 between the etrasimod treatment group (34%) and the placebo treatment group (14%). Alternatively, based on the same assumptions, using normal approximation to the binomial distribution, a two-sided test would achieve at least 90% power. The assumptions are based on the final analysis results in the Phase 3 Studies APD334-301 and APD334-302. Sample size is calculated using the EAST® software.

At the time of this amendment, approximately 45 subjects among the already randomized subjects (assuming approximately 2:1 ratio of etrasimod placebo) do not meet the amended Inclusion Criterion 5 in Study APD334-210 protocol amendment 2.0, which includes ES score ≥ 2 and RB score ≥ 1. As a result, these subjects will be excluded from the Primary Analysis Set (refer to section 10.3) but these subjects will be included in other analysis sets as deemed appropriate. Therefore, approximately 225 total subjects (150 etrasimod, 75 placebo) are required to be enrolled into study.

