Treatment-emergent adverse events (TEAEs) in the 1 mg, 2 mg, and placebo groups were reported for 59.6%, 56.0%, and 50.0% of subjects, respectively; treatment-related TEAEs were reported for 7.7%, 10.0%, and 5.6% of subjects, respectively; serious adverse events (SAEs) were reported for 5.8%, 0%, and 11.1% of subjects, respectively; and TEAEs leading to discontinuation of study treatment were reported for 5.8%, 8.0%, and 0% of subjects, respectively. No subjects died during the study. Overall, the 2 mg dose demonstrated a favorable safety profile and was chosen as the dose for the current Phase 2 program.

The primary endpoint of clinical remission at Week 52, as assessed using the modified Mayo Score (MMS), is a standard, widely used index. In this study, clinical remission and response endpoints, unless otherwise noted, will be based on MMS. Other endpoints for the study are widely used and considered reliable measures of efficacy and safety.

As detailed in Section 10.2, the study is powered to the primary endpoint for demonstrating a statistically significant difference in clinical remission between etrasimod therapy and placebo at Week 52. The 2:1 randomization scheme will maximize the number of subjects receiving a potentially beneficial therapy.

Subjects meeting predefined eligibility criteria from the end of the 12-Week Treatment Period and during the 40-Week Treatment Period will be eligible to enter the APD334-303 OLE study (Section 5.1.1).

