10.12.1. Efficacy Analysis

The primary analysis of the binary efficacy endpoints will be carried out using the Cochran-Mantel-Haenszel (CMH) method, stratified by (a) naïve to biologic or JAK inhibitor therapy at study entry (yes or no) and (b) baseline corticosteroid use (yes or no). The primary analysis will be based on Primary Analysis Set (refer to Section 10.3). Results will be expressed as the number of subjects in remission, remission percentages, difference in remission percentages, odds ratio, and associated 95% confidence intervals (CIs) and p-values.

There are multiple null hypotheses for the comparison of etrasimod and placebo in the primary and secondary efficacy endpoints. The family-wise type-I error rate will be controlled at the level of 0.05. The primary efficacy endpoint will be tested at a significance level of 0.05. Only if the primary null hypothesis is rejected, can significance claims proceed for the key secondary efficacy endpoints. The family of hypotheses and the multiple comparison procedure used to control the family-wise type-I error rate will be clearly specified in the SAP and may include some of other secondary efficacy endpoints.

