approximately 2:1 ratio of etrasimod:placebo) did not meet the amended Inclusion Criterion 5, which includes ES score ≥ 2 and RB score ≥ 1 . As a result, these participants will be excluded from the Primary Analysis Set (Section 4). Therefore, approximately 225 total participants (150 etrasimod, 75 placebo) were required to be enrolled into study C5041011 (APD334-210) under Protocol amendment 2.0.

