3.1.3. Derivation of Clinical Remission

The primary efficacy endpoint is clinical remission at Week 52. Based on above different derivation algorithms for RB/SF subscores, and different definitions for clinical remission, the clinical remission will be derived based on the following 3 approaches, respectively:

- Clinical remission 1, based on clinical remission definition per protocol and RB and SF derivation per protocol (Derivation 1, Section 3.1.1)
- Clinical remission 2, based on clinical remission definition per FDA Draft Guidance and RB and SF derivation per protocol (Derivation 1, Section 3.1.1)
- Clinical remission 3, based on clinical remission definition per FDA Draft Guidance and RB and SF derivation per FDA Draft Guidance (Derivation 2, Section 3.1.1)

Clinical remission 2 will be used for the primary analysis.

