5.2.1. Analyses for Binary Efficacy Endpoints

The primary analysis of all binary efficacy endpoints will be performed based on the Mantel–Haenszel (MH) weighted method, stratified by (a) naïve to biologic or JAK inhibitor therapy at study entry (yes or no) and (b) baseline corticosteroid use (yes or no). Results will be presented as the number of participants with response, proportion of participants with response, estimated common risk difference and associated two-sided 95% confidence intervals (CIs), and p-values from the MH weighted method.

For (a) and (b) mentioned above that are used in MH weighted method, the reported strata (which are based on randomization system) will be used for the statistical analyses. Analyses may be repeated using actual strata (which are based on medications reported in eCRF) if the strata data recorded in the randomization system and the actual strata data recorded in the

CRF are inconsistent for more than 10% of the randomized participants. i.e., if there are more than 10% of randomized participants whose reported strata are not the same as actual strata.

The methods for handling with missing data are described in Section 5.3 below.

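### Does the plan overstate its power by claiming at least 90% under the normal approximation?

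*Protocol*

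**What the plan says.** Protocol 10.2 takes "a two-sided significance level of 0.05, and a 2:1 randomization ratio" and Week 52 remission rates of 34% on etrasimod and 14% on placebo. On a two-group Fisher's exact test, "approximately 183 subjects (122 etrasimod, 61 placebo) are required to" reach at least 80% power. An alternative follows on the same assumptions: "using normal approximation to the binomial distribution, a two-sided test would achieve at least 90% power". The Synopsis and SAP 2.3 repeat this paragraph. None of the three names the variance formula.

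Protocol 3.2 refers back to this calculation: "As detailed in Section 10.2, the study is powered to the primary endpoint for demonstrating a statistically significant difference in clinical remission".

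About 45 subjects already randomized fall outside the Primary Analysis Set, so the enrolment target was raised; SAP 2.3 states that "approximately 225 total participants (150 etrasimod, 75 placebo) were required to be enrolled".

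On the analysis, Protocol 10.12.1 says "The primary analysis of the binary efficacy endpoints will be carried out using the Cochran-Mantel-Haenszel (CMH) method". SAP 5.2.1 instead specifies a stratified Mantel-Haenszel (MH) weighted analysis reporting the "estimated common risk difference and associated two-sided 95% confidence intervals (CIs), and p-values from the MH weighted method". SAP 3.1.3 fixes the endpoint version: "Clinical remission 2 will be used for the primary analysis". Neither document states a power for the stratified analysis.

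**The concern.** There are three grounds for doubt.

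- The 90% depends on which normal approximation is meant. The pooled-variance form gives a figure about five points lower at the same sample size.
- The figure is for an unstratified two-group test at 183 subjects. The primary analysis is stratified and will have about 180.
- The 34% and 14% rates carry no label saying which remission definition they reflect, although the SAP has moved the primary endpoint to the FDA draft guidance definition.

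A reader weighing a null or borderline result might take 90% as the power of the primary comparison and so underestimate the chance that a true 20-point difference was missed.

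**Working it through.** **Inputs.** Protocol 10.2 gives p1 = 0.34, p0 = 0.14, two-sided alpha 0.05, and n1 = 122, n0 = 61. The Primary Analysis Set is about 225 − 45 = 180, or 120/60 at 2:1.

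**Reproducing the stated figure (unpooled variance, 122/61).**

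- SE² = 0.14 × 0.86/61 + 0.34 × 0.66/122 = 0.001974 + 0.001839 = 0.003813, so SE = 0.06175.
- Power = Φ(0.20/0.06175 − 1.960) = Φ(1.279) = 89.95%.
- Placebo subjects needed for exactly 90%: (0.1204 + 0.2244/2) × (1.960 + 1.2816)²/0.04 = 61.1, so N = 3 × 61.1 = 183.3.

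The stated N of approximately 183 is what this formula returns for 90%. Of the standard variants tried, only this one reaches about 90%, so the unpooled form is an inference, though a secure one.

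**Other forms at 122/61.** For the pooled form, the average rate is (41.48 + 8.54)/183 = 0.2733 and the null SE is √(0.2733 × 0.7267 × (1/122 + 1/61)) = 0.0699. Power is Φ((0.20 − 1.960 × 0.0699)/0.06175) = 84.6%. This form would need N = 213.7 for 90%.

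| Test (34% vs 14%) | 122/61 | 120/60 |
|---|---|---|
| Unpooled normal approximation | 89.95% | 89.5% |
| Pooled normal approximation | 84.6% | 84.0% |
| Unpooled z test, exact power | 88.6% | 88.1% |
| Pooled z test, exact power | 85.1% | 84.9% |
| Fisher's exact, two-sided | 83.8% | 83.0% |

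Fisher's test first reaches 80% at 171 subjects (114/57, 80.3%), so the sizing criterion has room at both 183 and 180.

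**The planned analysis at 120/60.** The MH-weighted risk difference was simulated with 100,000 replicates per scenario, four strata, a common odds ratio and overall rates held at 34% and 14%. The stratum mixes, stratum effects and variance estimators are assumptions, because the documents give none of them.

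| Stratum effect (logit scale) | Greenland-Robins variance | Sato variance |
|---|---|---|
| None | 88.5–88.6% | 87.8–87.9% |
| Moderate (±0.5) | 88.6–89.3% | 88.1–88.6% |
| Strong (±1.0) | 89.3–90.9% | 89.0–90.4% |
| None to moderate, 2:1 not held within strata | 88.0–88.7% | 87.2–88.0% |

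A separate simulation with additive stratum effects agrees. It gives 87.7% to 88.6% with no effect, 88.2% to 89.3% with ±5 points, and 89.9% to 90.7% with ±10 points in four equal strata. Over both simulations, the range is 87.2% to 90.9%.

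**Scale of the gap.** Rounding of the two assumed rates to whole percentages matters more. At 122/61 the unpooled formula gives 86.4% for 33.5% against 14.5%, and 92.8% for 34.5% against 13.5%.

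**The rate label.** By SAP 3.1.2, the two remission definitions differ only when the stool frequency subscore at the visit is 1. The protocol then requires a drop of at least one point; the FDA-based definition requires only that it not exceed baseline. They disagree only for subjects with a stool frequency subscore of 1 both at baseline and at Week 52 who meet the bleeding and endoscopy conditions. The documents do not say how many such subjects to expect, so no shift in power can be calculated.

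**The case for a change.** The case for acting is that a power statement should be reproducible without guessing the formula and should describe the test that will be run. Here the reader must infer the unpooled form. The words at least are attached to a value just under 90% even on the most favourable form, and the exact power of that same test is 88.6%. For the MH analysis at about 180 subjects, the chance of missing a true 20-point difference is about 11% to 12% with no to moderate stratum effects. For the protocol's CMH test, power is about 84% to 86%. Two or three sentences in SAP 2.3 would clear this up.

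Part of this stands. The variance form is unnamed, about would be more accurate than at least, and the rates lack a definition label.

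The rest carries less weight. The sentence presents itself as an alternative, approximate calculation for a two-group comparison; it does not claim to be the power of the stratified analysis. Protocol 3.2 says the trial is powered as Section 10.2 describes without citing 90%, and the Fisher result satisfies that. An unpooled variance is the natural counterpart of an estimated risk difference with its confidence interval, which is what the SAP reports. The pooled and CMH figures belong to tests the SAP does not use, so they do not measure the gap. A simulated 88% in the SAP would replace a value anyone can recompute with one that rests on unstated strata.

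**Conclusion.** No change follows. The 90% is 89.95% under the unpooled normal approximation at 122/61, so it is a rounded figure and not an arithmetic error. Moving to 180 subjects costs about half a point on the same formula. For the planned MH risk difference the shortfall is mostly about 1 to 2 points with no to moderate stratum effects, reaches 2.8 points in the least favourable scenario, and disappears when the strata are strongly prognostic. Those figures assume true rates of 34% and 14%, about 180 subjects at 2:1, and the stratum mixes and variance estimators described above.

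The criterion that set the sample size, at least 80% by Fisher's exact test, is met at 183 and at 180. The SAP is dated July 2024 and speaks of the enrolment requirement in the past tense, so rewording the power statement would alter no decision. A null or borderline result would be judged on its estimate and confidence interval, which do not depend on this sentence. What remains is missing detail: the unnamed formula, at least where about is meant, and the unlabelled rates. The move from CMH in the protocol to MH weighting in the SAP is a separate matter and adds nothing to the size of this one.
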